6.1.4.1 Central Laboratory

Clinical laboratory tests will be analyzed centrally. Refer to the Laboratory Manual for information regarding collection, processing, and analysis of samples.

6.1.5 Vital Signs, Physical Findings and Other Safety Assessments

Vital signs, physical findings, and other safety assessments will be reviewed for results of potential clinical significance throughout the study. The Investigator will evaluate any changes. If the Investigator determines that a safety assessment is clinically significant, it is considered an AE. However, if the finding is consistent with the subject's current diagnoses, it may be documented accordingly.

6.1.5.1 Vital Signs

Vital signs (including blood pressure, pulse rate, respiratory rate, and temperature) will be recorded at the time points specified by Table 1.

If clinically significant findings, as determined by the Investigator, occur in any of the vital signs measurements, that measurement will be repeated at medically appropriate intervals until the value returns to an acceptable range, a specific diagnosis is established, or the condition is otherwise explained.

6.1.5.2 Physical and Neurological Examinations

The full physical examination will consist of the following: general appearance, skin, eyes, ears, nose, throat, neck, lymph nodes, chest, heart, abdomen, and extremities. All physical exams will also include an assessment of the subject's height and weight.

A brief neurological examination will consist of the following: mental status, cranial nerves, nystagmus, motor system, sensory system, reflexes, coordination, gait, and station.

The subject's developmental capabilities will be assessed as a part of the neurological examination (in a manner the Investigator sees fit) during the Screening Period (Visit 1) or Visit 2 (Day 1) only, whichever visit occurs first for each respective subject.

Additional examinations may be performed at the discretion of the Investigator.

6.1.5.3 ECGs

The ECGs will be performed at the time points specified in Table 1.

Subjects should be supine for ≥ 5 minutes prior to the assessment.

If the first ECG is abnormal, up to an additional 2 repetitions of a specific assessment may be performed.

6.1.5.4 C-SSRS

The Columbia-Suicide Rating Scale (C-SSRS) is a prospective assessment tool routinely used in studies of drugs with any potential for CNS effects. It captures the occurrence, severity, and frequency of suicide-related thoughts and behaviors during the assessment period. The risk of suicide will be evaluated using the C-SSRS for patients aged ≥ 7 years. Clinical impression will be used for patients < 7 years and for patients with development impairment for whom the C-SSRS would be inappropriate. The questionnaires will be completed at the time points specified by the schedule of assessments in Table 1.

6.1.5.5 Medical/Surgical History

A complete medical/surgical history will include evaluation (past or present) of the following: general, head and neck, eyes, ears, nose, throat, chest/respiratory, heart/cardiovascular, gastrointestinal/liver, gynecological/urogenital, musculoskeletal/extremities, skin, neurological/psychiatric, endocrine/metabolic, hematological/lymphatic, allergies/drug sensitivities, past surgeries, or any other diseases or disorders.

6.1.6 Safety-related Endpoints

The safety-related endpoints are:

- Incidence, type, and severity of AEs and SAEs associated with Cannabidiol Oral Solution as an adjunctive treatment for seizures
- Changes from baseline in the previous study in vital signs
- Changes from baseline in the previous study in ECG findings
- Changes from baseline in the previous study laboratory values (hematology, chemistry, and urinalysis).

6.2 Plasma Levels

Whole blood will be obtained in a Vacutainer® containing heparin anticoagulant for the determination of the plasma levels of cannabidiol and 7-OH cannabidiol in human plasma. The sample will be obtained as indicated in Table 1 prior to daily study medication dosing on that day. Samples for plasma level assessment of cannabidiol and 7-OH cannabidiol should

be collected immediately prior to administration of the morning dose of the investigational product on indicated days.

The following information will be captured for blood sample collection in each subject's eCRF:

- Subject number and initials
- Time and date of most recent administration of the investigational product prior to the sample collected for plasma level analysis
- Time and date of each blood sample collected for plasma level analysis
- Time and date of subject's ingestion of food (i.e., the evening meal on the day prior to each study visit).

Samples for the determination of the investigational product in human plasma will be analyzed by the Sponsor, using an appropriate bioanalytical method. It is anticipated that this will include estimates of concentration and trough (steady state) concentration of cannabidiol and 7-OH cannabidiol (monthly to quarterly). For subjects taking clobazam, levels of clobazam and its major metabolite (norclobazam) will be measured if there are safety concerns.

The analytical method for human plasma will be developed and validated. All samples still within the known stability of the investigational product will be analyzed.

Exploratory plasma samples will be shipped to the Sponsor or the Sponsor-designated bioanalytical laboratory.

6.2.1 Plasma Levels-related Endpoint

The plasma level-related endpoint is trough (steady state) concentrations of Cannabidiol Oral Solution throughout approximately 48 weeks of continuous exposure or until the investigational product is successfully approved for marketing in the US (whichever occurs earlier), inclusive of the subject's treatment on their previous study.

6.3 Efficacy

6.3.1 Seizure Control

In this study, seizure frequency, duration, and severity will be assessed to monitor seizure control achieved by long-term treatment with Cannabidiol Oral Solution. Seizures will be observed and recorded using a patient reported outcome (PRO) instrument (i.e.,

subject/caregiver diaries). The exact format and version(s) of diary to be used will also be included in the eCRF. Diaries will be dispensed at Visits 7, 8, and 9 (Weeks 12, 24, and 36) and reviewed and completed pages collected (if applicable) during each visit.

For the purposes of this study, only observable seizures will be quantified in the one week prior to Visits 8, 9, and 10. All seizures should be recorded by the parent(s)/caregiver(s) and/or subject (if applicable) in the diary.

Given that continuous seizures may be observed in some subjects (i.e., multiple seizures may occur without break), it may not be possible to accurately record all seizures for these subjects. If necessary, the parent(s)/caregiver(s) or subject (if applicable) will, at a minimum, categorize the seizure frequency (for seizures others than tonic or atonic seizures) by range (i.e., diaries will record the count of seizures per day as >50 seizures/day, 20 to 50 seizures/day, 6 to 19 seizures/day, 1 to 5 seizures/day, or no seizures).

The subject and/or his/her parent(s)/caregiver(s) are responsible for completing the diary. The party who is primarily responsible will be chosen by the Investigator in consultation with the subject's parent(s)/caregiver(s). If a pediatric subject will be entering diary data, the parent(s)/caregiver(s) should provide guidance and monitor accuracy and completeness.

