duration of treatment in INS011-14-030 will be based on the length of time they were enrolled in INS011-15-054 such that total duration of treatment in both studies combined will not exceed approximately 48 weeks. Subjects visit entry into INS011-14-030 will be determined at the discretion of the sponsor and the investigator.

The study will be terminated upon 1 of the following:

- The investigational product is successfully approved for marketing in the US
- Sponsor elects to terminate INS011-14-030.

Treatment with established background AEDs will continue without interruption and changes will be permitted as necessary based on safety concerns or due to changes in seizure control as described in Section 4.3.

As described in Table 1 and Section 5.0, visits will be scheduled at Week 1, Week 2, then monthly for 3 months, and then quarterly thereafter. A Screening Visit will be required for all subjects that do not rollover within 14 days of completing their previous study. All subjects will complete the Final Visit/ Discontinuation Visit regardless of when they stop treatment/complete the study. A Follow-up Visit will occur 2 weeks after the Final Visit/Discontinuation Visit.

At each visit, a record of the incidence and severity of adverse events (AEs), treatment-emergent AEs (TEAEs), and SAEs will be collected and this will serve as a primary outcome criterion for this study. Other safety-related parameters such as 12-lead ECG and hematology, chemistry, and urinary analyses will also be assessed at specified visits. Determination of trough plasma levels of cannabidiol and its 7-OH metabolite will be performed at each visit except Visits 3 and 4 (Week 1 and Week 2). This will support safety monitoring and establish the extent of variability during long-term treatment with the investigational product. For subjects taking clobazam, levels of clobazam and its major metabolite (norclobazam) will be measured if there are safety concerns. Seizure diaries will be reviewed to assess control of seizures (frequency, duration, and severity) throughout the duration of the study.

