4.2.1 Storage of the Investigational Product

The investigational product will be stored at controlled room temperature (20 to 25 degrees Centigrade, 68 to 77 degrees Fahrenheit) at the study center. The product can also be stored refrigerated (2 to 8 degrees Centigrade, 36 to 46 degrees Fahrenheit).

Cannabis and its constituents (including cannabidiol) are Schedule I controlled substances in the United States and subject to all applicable local and federal laws and regulations regarding these products. This includes security provisions for storing the controlled substances and for dispensing in a manner to prevent diversion. Additionally, the Sponsor or Investigator must provide a statement of the quantity to be manufactured and the sources of the chemicals to be used or the substance.

The DEA regulations detail specific security requirements for storage of the investigational product. Licensed practitioners must store controlled substances in a "securely locked, substantially constructed cabinet" and must notify the DEA of the theft or significant loss of any controlled substances within 1 business day of discovering such loss or theft.

Furthermore, all practitioners are prohibited from hiring employees who have been convicted of a drug-related felony or who have had a DEA registration denied or revoked.

Investigators are responsible for ensuring that all applicable licensures are in place and storage conditions are appropriate.

The investigational product will be dispensed from a Schedule I licensed study center.

Study centers are required to provide complete information, including eCRFs and final outcomes, on all instances of addiction, abuse, misuse, overdose, drug diversion/drug accountability, discrepancies in amount of the clinical supplies of the investigational product, noncompliance, protocol violations, lack of efficacy, individuals lost to follow-up, and any other reasons why subjects dropped out of the study.

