2.2. SECONDARY OBJECTIVES

The secondary objectives are:

- To establish the continued efficacy of Cannabidiol Oral Solution in maintaining seizure control in subjects with treatment-resistant seizures that previously completed INS011-14-029 or Part A (Visit 6) in INS011-15-054.
- To assess the global status of subjects taking Cannabidiol Oral Solution for an extended period of time determined by various qualitative assessments.
- To monitor for changes in plasma levels of cannabidiol and its 7-OH metabolite during long-term treatment of subjects with treatment-resistant seizure disorders, including LGS, DS and IS.

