9. DISPOSITION AND WITHDRAWALS

All subjects who provide informed consent will be accounted for in this study.

Subject disposition and withdrawals, and protocol violations, including inclusion and exclusion criteria will be presented for the ENR set.

The table will summarize the following information:

- Number of subjects screened
- Number of screen failures - overall and by following reasons:
 - subject did not meet eligibility criteria
 - Withdraw informed consent
 - Subject died
 - Other
- Number of treated subjects (SAF)
- Number of subjects in the PK
- Number of subjects who completed study including follow-up
- Number of subjects who discontinued from treatment (overall and by reasons)
- Number of subjects with early discontinuation from study (overall and by reasons)

For both discontinuation from treatment/study the reasons are as follows:

- Inadvertently enrolled (enrollment criteria not met)

Document: C:\Users\q832483\Documents\Insy CSR\Pending\Ready for QC\New folder\Statistical Analysis Plan.docx
Author: [REDACTED] Version Number: V1.0 Final
Version Date: 04APR2017

Template No: CS_TP_BS016 – Revision 3
Effective Date: 01May2012

Reference: CS_WI_BS005

- Investigator decision
- Adverse Event
- Subject withdrew consent
- Lack of protocol compliance
- Subject attempted suicide or is at risk of suicide
- Sponsor decision
- Subject becomes pregnant
- Abnormal laboratory values
- Lost to follow-up
- Death
- Other

The following important (clinically) protocol deviations, as identified in the clinical trial management system (CTMS), will be summarized:

- Administrative Criteria
- Eligibility and Entry Criteria
- IP Compliance
- Informed Consent
- Laboratory Assessment Criteria
- Serious AE Criteria
- Study Procedures Criteria
- Regulatory or Ethics Approvals Criteria
- Visit Scheduled Criteria
- Other Criteria

Supportive listings will also be provided:

- Allocation to treatment
- Protocol deviations
- Subjects eligibility criteria

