14. STUDY MEDICATION EXPOSURE

Exposure to study medication in days will be presented for the SAF, by age category and overall. The following parameters will be summarized:

- Modal dose (defined as the dose with the longest exposure),
- Total duration of study medication at any dose
- Total duration of each dose
- Number of subjects dosed per time points

The date of first study medication administration will be taken from the *Study Drug Administration* eCRF page. The date of last study medication will be taken from the *End of Treatment* eCRF page. In the case of missing data on these eCRF pages, the *Subject Diary – Study Medication Record* eCRF page will be used in order to determine the first and last date of study medication.

Interruptions, compliance, and dose changes are not taken into account for duration of exposure.

The corresponding listing will present first/last dose dates, does the subject complete the treatment duration, reason for end of treatment and duration of exposure (days).

In addition, dose modifications will be summarized by age category and overall in terms of:

- Number of subjects with at least one dose modification (as defined [Section 14.1](#))
- Number of subjects with at least one dose changed
- Number of subjects with at least one dose interrupted
- Number of subjects with dose permanently discontinued
- Number of subjects per reason of dose modification
 - Adverse event
 - Lack of efficacy
 - PK-analysis result
 - Other

If a subject experiences several dose modifications for the same reason, he will be counted only once for this reason. However, in the case a subject experiences several dose modifications due to different reasons, he will be counted once for each reason.

A supportive listing will display all the relevant administration details including data/time/interval of each administration, volume planned/administered, reason if dose not administered and amount of water consumed after dosing.

Exposure data coming from the *Subject Diary – Study Medication Record* eCRF page will also be listed.

Document: C:\Users\q832483\Documents\Insy CSR\Pending\Ready for QC\New folder\Statistical Analysis Plan.docx
Author: [REDACTED] Version Number: V1.0 Final
Version Date: 04APR2017

Template No: CS_TP_BS016 – Revision 3
Effective Date: 01May2012

Reference: CS_WI_BS005

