16.2.1.2. Missing Data Methods for Seizures-Related Variable(s)

All data will be evaluated as observed; no imputation method for missing values will be used.

The eCRF includes the following question on each study day: "Did the subject experience any seizures?". If the response to this question is no, it will be assumed that the subject does not have any seizures on that day. If the question is not answered, it will be not assumed that the subject does not have any seizures that day (i.e., it will be assumed that the question is inadvertently not answered).

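### The seizure-count tables describe mainly subjects who remain to Week 24 or later, and no summary described in the SAP shows how many stopped for lack of efficacy

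*Protocol*

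**What the plan says.** **Objective.** SAP 2.2 lists as a secondary objective "To establish the continued efficacy of Cannabidiol Oral Solution in maintaining seizure control", and protocol 2.1 has the same aim. Both documents also say that efficacy data are not endpoints, and the analysis is descriptive.

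**Counting.** Protocol 6.3.1: "only observable seizures will be quantified in the one week prior to Visits 8, 9, and 10". The same section says "Diaries will be dispensed at Visits 7, 8, and 9 (Weeks 12, 24, and 36"), and protocol 5.2.4 likewise places the first dispensing at Visit 7. Protocol 3.1 reads more widely: "Seizure diaries will be reviewed to assess control of seizures (frequency, duration, and severity) throughout the duration of the study".

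**Analysis.** SAP 16.2.1 gives the seizure time points as Week 24, Week 36 and the final visit. SAP 16.2.1.2: "All data will be evaluated as observed; no imputation method for missing values will be used".

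**Reasons for stopping.** SAP 9 introduces its list with "For both discontinuation from treatment/study the reasons are as follows". Twelve reasons follow, and lack of efficacy is not among them. Protocol 4.2.1 requires sites to give complete information on, among other things, "noncompliance, protocol violations, lack of efficacy, individuals lost to follow-up, and any other reasons why subjects dropped out of the study". SAP 14 plans "Number of subjects per reason of dose modification", with four reasons, one of which is lack of efficacy. SAP 14.1 defines a modification as a dose change, an interruption or a permanent discontinuation.

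**The concern.** Whether control is maintained depends partly on the subjects in whom it was not, and some of these can be expected to leave. If they leave before a diary week, they have no value in the seizure tables, and a mean over those who stayed can improve simply because poor responders have gone. A reader would then look to disposition to see how many left for loss of effect. That number is not shown there, and the one table that names lack of efficacy combines stopping with dose adjustment. Treatment is open-label, and both study dose and background AEDs may be adjusted. With at most 80 subjects split into three age categories, a few early leavers can move a group mean.

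**Working it through.** **1. The plan's own figure.** Protocol 3.4 and 8.1 give maxima of 60 and 20 rollover subjects; 60 + 20 = 80, as stated. There is no power calculation, and neither a dropout rate nor an expected response rate is given.

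**2. Scheduled coverage.**
- Diary days: 3 × 7 = 21. Treatment days: 48 × 7 = 336. 21/336 = 6.25%.
- The target for Visit 8 is Day 168 (SAP 6.4, Table A). The diary week is Days 161 to 167, so Days 1 to 160 have no scheduled count: 160/336 = 47.6%.
- With the ±10-day visit window, Visit 8 falls on Days 158 to 178, and 150 to 170 days are uncounted (44.6% to 50.6%).
- These figures apply to entry at Visit 2. Subjects from INS011-15-054 may enter at a later visit.

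**3. Who has a count, by time of stopping.**

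| Stops | On-study seizure count |
|---|---|
| Before Week 12 | None: no diary yet dispensed (protocol 5.2.3, 5.2.4, 6.3.1) |
| Weeks 12 to 24 | Possible: diary in hand, collected at the discontinuation visit if applicable (protocol 5.3) |
| After Visit 8 | Week 24 count, if the diary was completed |

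Protocol Table 1 marks dispensing in a column that merges Visits 5, 6 and 7. I follow the section text, which places it at Visit 7.

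For the middle row, recording is tied to the week before a quarterly visit, as is the recommended reminder call (protocol 4.6). An unplanned stop may come before any diary week.

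**4. Where an early count would go.** Table A ends Week 12 at Day 91 and starts Week 24 at Day 158, so Days 92 to 157 (66 days) have no window. SAP 6.3 maps early-termination data to the next available visit. SAP 6.4 says only that the final or discontinuation visit date should match the last diary record. The SAP does not say which rule governs a diary from those 66 days.

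**5. Where stopping for lack of efficacy could appear.**
- SAP 9: no category.
- SAP 14 summary: subjects are counted once per reason, and type of modification is counted separately. Reason is not crossed with type, so stops cannot be separated from dose changes.
- SAP 14 listing: reason for end of treatment by subject, which is not a summary.
- SAP 16.2.1.3: no row for subjects already discontinued, and no stated denominator for its percentages.

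**6. What the denominator can do (illustration only).** Let a share d of all treated subjects leave with no count because of lack of effect, and let a share p of the rest keep control. The observed-case share is p. The all-treated share, with leavers counted as not controlled, is p(1 − d). The gap is p × d. Both inputs are assumptions.

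| d (of 80) | Gap for p = 0.40 to 0.60 |
|---|---|
| 5% (4) | 2 to 3 points |
| 10% (8) | 4 to 6 points |
| 20% (16) | 8 to 12 points |
| 30% (24) | 12 to 18 points |

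The SAP plans no such proportion, so this shows sensitivity to the denominator and does not predict a planned table.

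**The case against.** A reader might infer that seizures are counted only in subjects still attending, that lack of efficacy is nowhere recorded as a reason for stopping, and that loss of control therefore vanishes from the trial. The documents do not support this:

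- Every subject is to have a discontinuation visit whenever they stop. The diary is collected there if applicable, and early-termination data are kept in by-visit summaries (protocol 5.3, SAP 6.3). Some who leave after Week 12 can contribute. Subjects who stop treatment may also complete the remaining visits (protocol 3.4.3).
- SAP 14 does tabulate lack of efficacy, and its definition of modification includes permanent discontinuation. A listing gives each subject's reason for end of treatment, which is readable with at most 80 subjects.
- CGI is rated by investigator and caregiver at Weeks 4, 8 and 12 and at discontinuation. SAP 16.2.2.2 keeps withdrawn subjects in up to withdrawal.
- Seizures that differ significantly from baseline, and new seizure types, are AEs (protocol 6.1.1). Seizure and status epilepticus are AESI terms (SAP Appendix 2).
- Efficacy data are not endpoints, and the one-week diary was a deliberate choice recorded in the amendment history.

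All of this limits the point, but a gap remains. No diary exists before Week 12 for the mapping rule to act on. SAP 14 does not separate stops from dose changes. CGI is a global rating and is not linked to the seizure tables. The AE rule does not say which baseline is meant; if it is the pre-treatment level, a subject who loses benefit and returns to that level has no AE. Declining to call efficacy an endpoint does not remove the stated objective.

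**Conclusion.** The concern holds as a limit on what the seizure-count tables describe and as a reporting gap. As described in the SAP, the tables cannot show how many subjects stopped for lack of efficacy, although sites must report it. CGI, AE/AESI and dose-modification data give partial information on early loss of control.

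The size of any bias cannot be derived. The coverage figures (6% of days counted, about 48% before the first count) measure how much is observed; they are not estimates of selection. It would also go too far to say that leavers are filed under consent withdrawal, investigator decision or other: some may be coded as adverse events, and the rest is inference.

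The conclusion assumes that the section text governs diary dispensing and that the SAP text reflects the planned summaries. The output templates and eCRF pages were not available to check. The change is worth making before database lock.

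**What to change.** 1. **SAP 9 and the eCRF code list:** add lack of efficacy to the reasons for discontinuing treatment and study. Map earlier cases from the dose-modification reason and any recorded text.
2. **SAP 14:** cross-tabulate reason by type of modification (changed, interrupted, permanently discontinued).
3. **SAP 16.2.1.3:** at each time point, show the number of Safety Population subjects with a count and the number already discontinued, by reason. Label the means as applying to subjects with a diary.
4. **Supportive row only:** among Safety Population subjects with tonic or atonic seizures at Baseline 1, give the proportion no higher than Baseline 1, counting lack-of-efficacy discontinuations as not maintained. The restriction is needed because a subject with none at baseline and none later would otherwise score as maintained. Infantile spasms are recorded as myoclonic, so this row does not cover them.

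These are recording and reporting changes. They alter neither the diary schedule nor any rule for stopping treatment, so the period before the first diary week stays uncounted. Protocol 8.2.1 lets statistical changes made before lock be documented in the SAP without a protocol amendment. The cost is SAP wording, one code-list entry, a few extra table rows and possibly a less favourable efficacy picture.
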